### Post hoc analyses.

In the event that investigators or reviewers introduce analyses in addition to those described above, these will be clearly delimited as *post hoc* and will be considered hypothesis-generating.

## PRESENTATION OF THE RESULTS

After completion of enrollment and data analysis, the results of the trial will be communicated to the public through manuscript publication and submission of the results to clinicaltrials.gov. Submission for publication will include public access to the full study protocol and statistical code. Authorship will be based on the International Committee of Medical Journal Editors guidelines and professional writers will not be used.

The flow of patients through the study will be presented in a flow diagram (Figure 2). Baseline characteristics will be presented by treatment group, as shown in Table 1 and Table E2. The volume of isotonic crystalloid administered, other fluids, and blood products administered over time will be presented by treatment group (Table E3). Serum values for sodium, potassium, chloride, bicarbonate, blood urea nitrogen, and creatinine will be presented in figures displaying serum values over time by group and in tables detailing the incidence of abnormal values (Table E4). Clinical and renal outcomes will be reported by treatment group, as shown in Table 2. For the primary analysis of the primary outcome, we will present the unadjusted frequency and proportion of MAKE30 in each study group as well as the adjusted odds ratio, 95% confidence interval, and *P* value derived from the generalized linear mixed-effects model. Indications for new renal replacement therapy will be displayed as in Table E5. Heterogeneity of treatment effect analyses will be displayed as loess curves or partial

effect plots for continuous variables and forest plots for categorical variables.

## DISCUSSION

Upon completion, SMART will provide the most comprehensive data to date on the comparative effects of saline versus balanced crystalloids among critically ill adults. Given that isotonic crystalloid administration represents the most common intervention provided to hospitalized patients, saline and balanced crystalloids are the only available options for isotonic crystalloid administration, and the relationship between saline and acute kidney injury and death remains unclear, the results of SMART will have immediate implications for the care of a broad population of acutely ill patients. Results showing superior clinical outcomes in the balanced crystalloids group would provide compelling evidence that balanced solutions should be considered the preferred isotonic crystalloid for most acutely ill patients. Better clinical outcomes with saline would cement 0.9% sodium chloride as the first line isotonic intravenous fluid and end the current debate about optimal crystalloid composition. In this comparative effectiveness trial of thousands of critically ill adults, a finding of no difference between groups would still have important implications for clinical care and future research. In a trial powered to detect absolute risk reductions as small as 2% in clinical outcomes, no difference between groups would imply that the effect of crystalloid choice for the majority of ICU patients is minimal and any future research would need to focus on select subpopulations.

While designing SMART, we weighed the relative advantages and disadvantages of multiple study designs, including a blinded, patient-level randomized trial. A major challenge to controlled studies of fluid administration in critical illness is the ability to enroll patients prior to the period of highest fluid exposure. As the majority of fluid is administered as part of resuscitation in the emergency department and first 12 hours of ICU admission, we selected a cluster-level-allocation design that would allow enrollment immediately upon presentation and coordination between study ICUs and the emergency department to maximize exposure to the assigned crystalloid and minimize exposure to the non-assigned crystalloid. By basing study group assignment at the unit level, we ensured delivery of the assigned crystalloid even among unstable patients for

whom fluid was being administered immediately upon presentation, since the assigned crystalloid would be the fluid most readily available in the study unit. The enrollment of all adults admitted to the participating ICUs examines the effects of saline versus balanced crystalloids in a real-world, clinical environment improving the generalizability of the study findings. Coupling group assignment at the level of the ICU with relatively short periods (one month) and frequent crossovers (at least eleven in each unit) balances baseline characteristics and co-interventions better than a simple cluster-randomized trial or before-after trial with the same number of units, decreasing confounding by seasonal change or trends in usual care over time. Although blinding of treating clinicians and study personnel to the assigned intervention would be ideal, a prior pilot trial of the same topic found high rates of provider awareness of crystalloid assignment despite blinding, perhaps due to the overt effect of the study crystalloids on clinically available laboratory values such as serum chloride and bicarbonate[13]. Use of an objective, patient-centered primary outcome abstracted automatically from the EHR increases the pragmatic nature of the design and diminishes the risk of observer bias.

Several potential threats to the validity of our trial exist. Including all patients admitted to each study ICU may produce a patient population with limited average exposure to the study interventions[13,14]. Based on our preliminary data from the same units prior to this study, however, we anticipate that more than 90% of enrolled patients will receive isotonic crystalloid and at least 25% of patients will receive more than 4 liters of isotonic crystalloid, which is comparable or greater than that received in prior positive ICU fluid trials[30]. Additionally, we have pre-specified analyses to evaluate for a 'dose-response' relationship between the volume of isotonic crystalloid administered and clinical outcomes with saline vs balanced crystalloid. Similarly, the broad enrollment criteria may produce a study population at relatively low risk for adverse clinical outcomes. The anticipated incidence of the primary outcome of 15%, however, is comparable to that of other large ICU fluid management trials[30,31]. Treating clinicians are aware of study group assignment which may permit a treatment bias in which clinicians administer less isotonic crystalloid and/or more non-isotonic crystalloids when assigned to one of the fluid groups. For this reason, we will record

and report not only use of isotonic crystalloid but non-isotonic crystalloid, colloid, and blood product during the trial. Group assignment at the level of the cluster with multiple cluster-level crossovers introduces the possibility for intra-cluster correlation, inter-period correlation, and intra-cluster intra-period correlation which may confound the relationship between group assignment and clinical outcome. In preparatory analyses using data from more than 10,000 patients admitted in the year prior to the trial, we have found the effect of intra-cluster correlation to be minimized by the short periods and frequent crossovers and the effects of intra-period correlation and intra-cluster intra-period correlation to be small. Our primary analysis uses a generalized linear mixed-effects model to account for these aspects of the study structure. In the absence of a washout period, there will be carryover of crystalloid administration from one group assignment into the other, but based on pilot data we anticipate the volume of non-assigned crystalloid received as a result of carryover will be low[14], and we pre-specify secondary analyses to address the effects of carryover. Finally, although MAKE30 is a recommended outcome for clinical trials involving AKI[23,32], use of a composite outcome presents potential challenges. Unlike death and new receipt of renal replacement therapy, whether persistent renal dysfunction on hospital discharge is a patient-centered outcome remains a point of discussion. Persistent renal dysfunction also relies on the availability of serum creatinine measurements at baseline and before hospital discharge – potentially requiring imputation of missing data for one component of the composite primary outcome. Perhaps most importantly, although death, new receipt of renal replacement therapy, and persistent renal dysfunction are weighted equally in the MAKE30 composite outcome, they may not represent equivalent outcomes to patients or providers. To address this we will provide data on the MAKE30 outcome overall and each of its separate components.

## **TRIAL STATUS**

In summary, SMART is an ongoing pragmatic cluster-level-allocation, cluster-level-crossover trial that will compare saline to balanced crystalloids with regard to major adverse kidney events among critically ill adults. Patient enrollment began June 1, 2015, and enrollment is scheduled for completion on April 30, 2017.

## LIST OF ABBREVIATIONS

CTSA	Clinical and Translational Science Award
CONSORT	Consolidated Standards of Reporting Trials
dL	deciliter
DSMB	data and safety monitoring board
ED	emergency department
EHR	electronic health record
IRB	institutional review board
ICU	intensive care unit
IV	intravenous
KDIGO	Kidney Disease Improving Global Outcomes
L	liter
MAKE30	Major Adverse Kidney Event by Day 30
mg	milligram
ml	milliliter
RRT	renal replacement therapy
SMART	Isotonic Solutions and Major Adverse Renal Events Trial

## DECLARATIONS

**Ethics Approval and Consent to Participate:** The trial was approved by the Vanderbilt University Medical Center Institutional Review Board (IRB) with waiver of informed consent (IRB#141349).

**Availability of Data and Material:** A file containing the de-identified data needed to replicate the primary analysis will be submitted as a supporting file at the time of submission of the main manuscript for the trial. The complete dataset developed during the current study will be available from the corresponding author upon reasonable request.

**Funding:** Funding was provided by the Vanderbilt Institute for Clinical and Translational Research (UL1 TR000445 from NCATS/NIH). [name] was partially supported by a National Heart, Lung, and Blood Institute (NHLBI) T32 award (HL087738 09). [name] was partially supported by the National Institute of General Medical Sciences (NIGMS) award K23GM110469. The funding institutions had no role in (1) conception, design, or conduct of the study, (2) collection, management, analysis, interpretation, or presentation of the data, or (3) preparation, review, or approval of the manuscript.

## FIGURES

**Figure 1.**

[figure not shown]
**Crystalloid assignment during the trial.** During each month of the study, each ICU is assigned to use either 0.9% saline (S) or balanced crystalloids (B).

	Jun	Jul	Aug	Sept	Oct	Nov	Dec	Jan	Feb	Mar	Apr	May	Jun	Jul	Aug	Sept	Oct	Nov	Dec	Jan	Feb	Mar	Apr
	2015							2016												2017			
Medical	S	B	S	B	S	B	S	B	S	B	S	B	S	B	S	B	S	B	S	B	S	B	S
Neuro					B	S	B	S	B	S	B	S	B	S	B	S	B	S	B	S	B	S	B
Cardiac							B	S	B	S	B	S	B	S	B	S	B	S	B	S	B	S	B
Trauma										B	S	B	S	B	S	B	S	B	S	B	S	B	S
Surgical													B	S	B	S	B	S	B	S	B	S	B

**Figure 2.**

**Flow diagram of the progress of patients through the trial.**

ICU = intensive care unit.

## TABLES

**Table 1. Patient characteristics at baseline.**

Patient Characteristics	Saline (n =)	Balanced (n =)
Age, median [IQR], years	--	--
Men, No. (%)	--	--
Caucasian, No. (%)	--	--
Weight, median [IQR], kg	--	--
Body mass index, median [IQR], kg/m 	--	--
Renal comorbidities, No. (%)		
Chronic kidney disease, stage III or greater	--	--
Prior renal replacement therapy receipt	--	--
Source of admission to ICU, No. (%)		
Emergency department	--	--
Transfer from another hospital	--	--
Hospital ward	--	--
Another ICU within the hospital	--	--
Operating room	--	--
Outpatient	--	--
Study ICU, No. (%)		
Medical	--	--
Surgical	--	--
Cardiac	--	--
Neuro	--	--
Trauma	--	--
Admitting diagnosis, No. (%)	--	--
Sepsis or septic shock	--	--
Traumatic brain injury	--	--
Mechanical ventilation, No. (%)	--	--
Vasopressors, No. (%)	--	--
UHC expected mortality, mean (95% CI), %	--	--
Serum creatinine, median [IQR], mg/dL		
Lowest in 12 months prior to hospitalization	--	--
No. (%) of patients	--	--
Lowest between hospitalization and ICU admission	--	--
No. (%) of patients	--	--
Estimated by three-variable formula	--	--
No. (%) of patients	--	--
Study baseline	--	--
Acute kidney injury, stage II or greater	--	--

**Table 2. Clinical Outcomes.**

Outcome	Saline (n =)	Balanced (n =)	Adjusted OR (95% CI)	Adjusted P Value
Primary Outcome				
Major Adverse Kidney Event within 30 days, No. (%)	--	--	--	--
Secondary Clinical Outcomes				
In-hospital mortality, No. (%)				
Before ICU discharge	--	--	--	--
Before 30 days	--	--	--	--
Before 60 days	--	--	--	--
ICU-free days, median [IQR]	--	--	--	--
Mean ± SD	--	--		
Ventilator-free days, median [IQR]	--	--	--	--
Mean ± SD	--	--		
Vasopressor-free days, median [IQR]	--	--	--	--
Mean ± SD	--	--		
Renal replacement therapy-free days, median [IQR]	--	--	--	--
Mean ± SD	--	--		
Secondary Renal Outcomes				
Serum creatinine, mg/dL				
Highest before discharge or day 30, median [IQR], mg/dL	--	--	--	--
Change from baseline to highest value, median [IQR], mg/dL	--	--	--	--
Final value before discharge or 30 days, median [IQR], mg/dL	--	--	--	--
Among survivors, median [IQR], mg/dL	--	--	--	--
Final creatinine > 200% baseline, No. (%)	--	--	--	--
Among survivors to hospital discharge	--	--	--	--
Among survivors to hospital discharge without new RRT	--	--	--	--
Acute kidney injury, stage II or greater, No. (%)	--	--	--	--
Developing after enrollment	--	--	--	--
Receipt of new renal replacement therapy, No. (%)	--	--	--	--
Duration of in-hospital receipt, median [IQR], days	--	--	--	--
Continued receipt after hospital discharge, No. (%)	--	--	--	--

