### Study Hypotheses:

- Primary: Use of balanced crystalloids for intravenous fluid administration among ICU patients will decrease the development of MAKE30 compared with use of saline
- Secondary: Use of balanced crystalloid for intravenous fluid administration among ICU patients will decrease the incidence of in-hospital mortality, decrease the incidence of acute kidney injury, decrease the incidence of new RRT, and decrease the incidence of persistent renal dysfunction.

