#### **Secondary Endpoints:**

1. In-hospital mortality before ICU discharge, before 30 days, and before 60 days
2. ICU-free days to day 28
3. Ventilator-free days to day 28
4. Vasopressor-free days to day 28
5. Renal replacement therapy-free days to day 28
6. Incidence of new RRT
7. Duration of new RRT
8. Incidence of persistent renal dysfunction
9. Incidence of Stage II or greater AKI by KDIGO creatinine criteria
10. Highest serum creatinine value
11. Change from baseline to highest serum creatinine value
12. Final serum creatinine value before hospital discharge or 30 days

Principal Investigators: [name], [name]

Version Date: 6/15/17

Study Title: Isotonic Solutions and Major Adverse Renal Events Trial (SMART)

Institution/Hospital: Vanderbilt University Medical Center

13. Serum values for sodium, potassium, chloride, bicarbonate, blood urea nitrogen, and creatinine from enrollment through hospital discharge or 30 days
14. *Urinary biomarkers of pre-renal and intra-renal acute renal failure*
15. *Serum biomarkers of intravascular volume overload and acute renal failure*

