### **Statistical Analysis Principles**

All analyses will be performed using R version 3.2.0 (R Foundation for Statistical Computing, Vienna, Austria). To maximize transparency and reproducibility, a complete version of the R code that will be used to analyze the final study data is available in Additional File 1. This ensures that (1) statistical reviewers or external investigators will be able to replicate the pre-specified analysis of the trial independently and (2) any changes or additions to the statistical analysis introduced by investigators or reviewers after completion of enrollment will be evident as differences between the pre-specified code and the analysis code included with the final publication.

All analyses will be conducted at the level of the individual patient during an individual hospitalization in an intention-to-treat fashion unless otherwise specified. Continuous variables will be reported as mean  $\pm$  standard deviation, mean and 95% confidence interval, or median and interquartile range; categorical variables as frequencies and proportions. Between-group comparisons will be made with the Mann-Whitney rank sum test for continuous variables, chi-square test for categorical variables, generalized estimating equations for repeatedly measured variables, and generalized linear mixed-effects models for analyses of the primary and secondary outcomes. A two-sided  $P$  value  $< 0.05$  will be considered to be statistically significant.

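### SAP Table 2 plans adjusted odds ratios and P values in subsets defined by survival and new RRT, which the fluid is hypothesised to change; these rows should be descriptive only

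*Combined protocol and SAP*

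**What the plan says.** SAP Table 2 (Clinical Outcomes) has one column per arm, then an adjusted odds ratio with confidence interval, then an adjusted P value. Five rows with all four cells marked concern patients selected by what happened after enrollment:

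- final creatinine value, "Among survivors, median [IQR], mg/dL";
- final creatinine above 200% of baseline, "Among survivors to hospital discharge";
- the same outcome, "Among survivors to hospital discharge without new RRT";
- under receipt of new RRT, "Duration of in-hospital receipt, median [IQR], days";
- also under receipt of new RRT, continued receipt after hospital discharge.

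In the same table the mean and SD rows leave the last two columns blank, so the shell does separate descriptive rows from inferential ones. Statistical Analysis Principles specifies "generalized linear mixed-effects models for analyses of the primary and secondary outcomes", and Presentation of the Results says that clinical and renal outcomes follow Table 2. Protocol section 8.5 (version 6/15/17) lists "Duration of new RRT" as a secondary endpoint. No text labels the five rows descriptive or states what effect they estimate.

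Protocol section 1.0, Study Hypotheses, says that balanced crystalloid "will decrease the incidence of in-hospital mortality, decrease the incidence of acute kidney injury, decrease the incidence of new RRT".

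**The concern.** Death and new RRT decide who enters these rows, and both are components of the primary outcome. If balanced crystalloid prevents some deaths, its survivors include patients whose counterparts in the saline months died and dropped out of the row. Those extra patients plausibly have worse kidneys. The model's covariates describe patients at or around ICU admission and cannot remove selection that happens afterwards. A fluid that saves lives could then appear to harm the kidneys of survivors. Dropping RRT recipients as well selects a second time.

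The two RRT rows raise a related problem. A fluid that prevents some courses of RRT changes the mix of patients who receive it, and death ends RRT early.

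The SAP recognises this problem in another place: under Main Secondary Analysis it notes that crystalloid volume arises after enrollment, and it adds three sensitivity analyses. Table 2's restricted rows get none.

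**Working it through.** **The plan's own figure.** The plan gives no figure for these rows. Its primary power statement (14,000 patients, MAKE30 about 15%, 1.9-point difference, 90% power) reproduces at 89.9% for 15.0% against 13.1% with 7,000 per arm and no clustering term. It does not bear on this point, except that its 12% relative reduction is a useful benchmark.

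**Survivor row: inputs.** Only the sample size has a source in the documents: at least 15,000 patients (protocol, Final Anticipated Sample Size), so 7,500 per arm. The rest are assumptions:
- saline mortality m = 11%;
- final creatinine at or above 200% of baseline in r = 5% of patients who survive on either fluid, with no effect of fluid on it;
- balanced crystalloid saves d = 0.5, 1.0 or 1.5 points of mortality and causes no deaths;
- a proportion q of those saved, from 5% to 50%, have dysfunction.

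**Formulas.** The rate among saline survivors is r. Among balanced survivors it is p = [(1 − m)r + dq] / (1 − m + d). The spurious odds ratio is [p/(1 − p)] / [r/(1 − r)]. Rejection is two-sided at 0.05, from the normal approximation to the log odds ratio, without clustering or covariates.

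**One case in full (d = 1.0 point, q = 30%).** p = (0.89 × 0.05 + 0.01 × 0.30) / 0.90 = 0.0475 / 0.90 = 0.0528. The odds ratio is (0.0528/0.9472) / (0.05/0.95) = 1.059. Survivors number 7,500 × 0.89 = 6,675 and 7,500 × 0.90 = 6,750. The standard error of the log odds ratio is 0.078, z = 0.73, and rejection is 11.3%.

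**Range (odds ratio; rejection rate).**

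| Dysfunction in those saved | 0.5 point saved | 1.0 point saved | 1.5 points saved |
|---|---|---|---|
| 5% | 1.00; 5.0% | 1.00; 5.0% | 1.00; 5.0% |
| 10% | 1.01; 5.1% | 1.01; 5.2% | 1.02; 5.6% |
| 30% | 1.03; 6.6% | 1.06; 11.3% | 1.09; 19.1% |
| 50% | 1.05; 10.1% | 1.11; 25.5% | 1.16; 48.3% |

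The 1.5-point column is a relative mortality reduction of 1.5/11 = 13.6%, slightly above the 12% benchmark, which would be 0.12 × 11 = 1.3 points.

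**Survivors without new RRT.** Use the same method with 7,000 per arm, mortality 10%, new RRT in k = 2% to 4%, a 12% relative reduction in each, r = 4%, dysfunction in 10% to 50% of those saved from death and in 30% to 70% of those spared RRT (all assumed apart from the 12% and the 7,000). With k = 3% and the middle rates of 30% and 50%, p = (0.87 × 0.04 + 0.012 × 0.30 + 0.0036 × 0.50) / 0.8856 = 0.0402 / 0.8856 = 0.0454, and the odds ratio is 1.14. The range is 1.04 to 1.26. It falls to 1.00 if those saved or spared have the same 4% as everyone else.

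**RRT duration.** Assume 140 to 280 recipients per arm (2% to 4% of 7,000), lognormal duration with median 6 days, 12% of courses avoided on balanced crystalloid, and no change in any treated patient. In 600 simulated trials per setting:
- if the avoided courses are a random 12%, the median stays at about 6.0 days in both arms and rejection is about 4% to 5%;
- if they come from the shorter half, the balanced median rises to 6.8 to 6.9 days and rejection is 16% to 27%.

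These runs do not model death during RRT.

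**The case against.** The strongest reply is that the plan already limits the damage. The all-patient rows for final creatinine, final creatinine above 200% of baseline, new RRT and RRT-free days sit in the same table with their own odds ratio and P value cells. Appendix 2 scores death before day 28 as 0 RRT-free days. The survivor-restricted creatinine rows are not listed endpoints. Comparisons of secondary outcomes are declared hypothesis-generating. All of this stands and keeps the point minor. It does not make a restricted odds ratio unbiased, because the hypothesis-generating clause deals with multiplicity and not with selection.

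A second reply is that the plan to test these rows is read from a table shell. The contrast with blank mean and SD cells holds in SAP Table 2 but not in Table 2 of the published protocol, where the mean and SD rows carry dashes in every column and some parent rows carry none. That may be an effect of reading the PDF. The restricted rows are marked in both versions, but the argument from layout rests on the SAP table, together with the SAP's general text on models and presentation.

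Third, restriction to recipients is inferred for the two RRT rows. They are nested under receipt of new RRT and Appendix 2 does not define duration. A median over all patients would be 0 with so few recipients, so the inference is reasonable for duration, but it is not written.

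**Conclusion.** The point holds as a minor analysis and labelling issue. Following Table 2 as laid out would give effect estimates in subsets formed by outcomes that the fluid is hypothesised to change. For the survivor row, selection alone gives an odds ratio of 1.00 to 1.16 and two-sided rejection of 5% to 48%, under the assumptions listed in the check.

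A reader might infer three stronger things that the documents do not support:

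- **That the survivor rows will show a sizeable false renal harm.** Rejection rates of 11% or more at 1.0 point saved need 30% to 50% dysfunction among those saved, six to ten times the assumed rate in other survivors. Nothing in the documents supplies that figure, and at 10% the bias is negligible.
- **That RRT duration is biased in a known direction.** The shift depends on which patients avoid RRT and on when deaths occur, and it may be nil.
- **That the main result is at risk.** MAKE30 is analysed in all patients and is unaffected.

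**What to change.** In Table 2, print the three survivor-restricted rows, RRT duration and continued RRT after discharge as counts or medians by arm, with no odds ratio, confidence interval or P value. Label them descriptive and state their denominators, including whether the two RRT rows are limited to recipients.

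Say in the SAP that inference on these questions rests on the all-patient analyses already planned: final creatinine at or above 200% of baseline (the SAP shell prints a strict inequality, unlike the definition), new RRT, RRT-free days with death scored 0, and MAKE30. An all-patient composite of death or final creatinine at or above 200% of baseline is optional; it is MAKE30 without its RRT component and uses data in hand.

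The cost is an edit to the table shell and a sentence or two of SAP text. The price is that a few secondary rows carry no P value. Sample size, data collection and the primary analysis do not change.
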